### 6.1. Primary outcome

For the primary outcome a General Linear Model (GLM) will be applied using  $\Delta$ liver fat (%) between month 12 and baseline as the dependent variable, treatment group as factor and type-2 diabetes status (yes/no), gender (male/female) and baseline liver fat content (%) as included covariates. The GLM will be applied for the ITT-population (defined above) as well as for the PP-population (defined above). Independent samples post-hoc t-tests will follow if between-group statistical significance is observed.

A sensitivity analysis will be conducted for the primary outcome in both the ITT- and PP-population, with weight change included as an additional covariate in the GLM.

Treatment effects will be presented as mean or median differences (%) with 95% confidence intervals and with corresponding p-values.

When assumptions of the GLM are not satisfied, the Willett's residual method will be applied, followed by Mann-Whitney U post-hoc tests.

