## **2.1. Sample size calculation**

The sample size calculation was based on Lehr's formula for comparison between two groups, assuming equal treatment effects for the two experimental diets. The standard deviation (SD) of the change in liver fat was 1.95 and 2.42 in two of our previous trials (1,2). As the population in the NAFLD trial will differ (e.g. higher prevalence of type 2 diabetes) compared to these other trials, we assume a SD of 3 for the current calculation. Given that 5% liver fat is the cut-off for NAFLD, we considered a 2% difference between groups as clinically relevant. To detect a difference of 2%-points in liver fat between the control group and one experimental group, n=36 individuals per group are needed with  $\beta=0.80$  and  $\alpha=0.05$ . To allow for 25% drop-out, n=50 individuals per group will be included. Thus, a total of n=150 individuals will be randomized.

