#### **5.2 Subgroups**

Further statistical analyses of the primary and secondary outcomes (liver fat, HbA1c and blood lipids) will be performed in the following prespecified subgroups:

**Type-2 diabetes status:** Subjects will be divided into two subgroups based on type-2 diabetes status (yes/no) of which the other subgroup (“no”) will constitute of subjects without type-2-diabetes but with prediabetes as defined by a fasting plasma glucose between 5.6-6.9 mmol/L and/or an HbA1c value between 39-47 mmol/mol. Type-2 diabetes diagnosis is verified by a clinician using medical records.

**Gender:** Subjects will be divided into two subgroups based on gender (male/female).

**NAFLD status:** Subjects will be divided into two subgroups based on NAFLD status (yes/no) in which NAFLD is defined as a liver fat content exceeding 5.56 % of liver tissue.

**PNPLA3 genotype:** Subjects will be divided into two subgroups based on the I148M variant of the PNPLA3 gene (CC vs CG/GG genotype).

**Compliers:** Subjects will be divided into two subgroups based on dietary adherence (high vs low compliers), assessed using both dietary and lipogenic biomarker changes (e.g. linoleic acid, DHA and palmitoleic acid) between month 0 and month 12.

All subgroup analyses will be conducted as described for the analyses of the full study population.

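### Pairwise diet comparisons are specified as unadjusted t-tests after a covariate-adjusted GLM, and the stated 80% power leaves out the omnibus step

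*SAP*

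**What the plan says.** **Model.** SAP section 6.1 models the change in liver fat with "treatment group as factor and type-2 diabetes status (yes/no), gender (male/female) and baseline liver fat content (%) as included covariates". There are three diets, so the group factor gives a test on 2 degrees of freedom.

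**Pairwise step.** One sentence covers it: "Independent samples post-hoc t-tests will follow if between-group statistical significance is observed". The SAP nowhere names an adjusted contrast or an estimated marginal mean.

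**Reporting.** "Treatment effects will be presented as mean or median differences (%) with 95% confidence intervals and with corresponding p-values". Whether these differences are adjusted is not stated.

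**Sensitivity analysis.** The primary analysis is repeated "with weight change included as an additional covariate in the GLM".

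**Reach.** Section 6.2 repeats the t-test sentence for secondary and exploratory outcomes. Section 5.2 carries the approach into the subgroups: "All subgroup analyses will be conducted as described for the analyses of the full study population".

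**Sample size.** In section 2.1, "The sample size calculation was based on Lehr's formula for comparison between two groups", on the assumption that both experimental diets work equally well. The result: "To detect a difference of 2%-points in liver fat between the control group and one experimental group, n=36 individuals per group are needed", at 80% power (printed as β) and α 0.05. The SD input is that of the change score: "The standard deviation (SD) of the change in liver fat was 1.95 and 2.42 in two of our previous trials", raised to 3 for this population. The three-arm omnibus test is not mentioned there.

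**The concern.** An independent-samples t-test has no covariates. Followed literally, the plan adjusts only the omnibus test, which says that some diets differ but not which. The question the trial was sized to answer, control against one experimental diet, is then settled without baseline liver fat or the two stratification factors.

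Three things follow.

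- The adjusted omnibus test and the unadjusted pairwise tests can disagree. The GLM may be significant while no pair of diets differs by t-test, although a contrast from the same model would show the difference.
- Adding weight change to the GLM can alter only the omnibus result. It cannot show whether a diet-versus-control difference persists after allowing for weight.
- Two analysts could report different primary estimates and intervals from the same data, both in keeping with the text.

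A separate point is that section 2.1 gives power for a direct two-group test, whereas section 6.1 reaches the pairwise test only after a significant omnibus test. The stated 80% is therefore not the power of the procedure that will be run.

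**Working it through.** **Inputs from the SAP.** Difference 2 points, SD of change 3, α 0.05 (taken as two-sided), 36 per arm needed, 50 per arm randomised, 25% drop-out, equal effects of the two experimental diets. Expected completers: 0.75 × 50 = 37.5, taken as 37.

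**Assumption.** The SAP does not say what share of the variance in change the covariates explain (R²). Values from 0 to 0.5 are shown.

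**1. The plan's own figure.** Lehr: n = 16 × (SD/difference)² = 16 × (3/2)² = 36 per arm, as stated. Drop-out: 36/0.75 = 48, rounded up to 50. Exact two-sample t-test power is 0.797 at n=36, 0.808 at n=37 and 0.910 at n=50. The arithmetic is right for a single direct test.

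**2. Precision.** The t-test keeps SD 3. A GLM contrast works with a residual SD of 3 × √(1 − R²), which is 2.68, 2.51 and 2.12 at R² 0.2, 0.3 and 0.5. The 95% CI width is about 2 × t × SD × √(2/37). For the t-test this is 2 × 1.99 × 3 × 0.2325 = 2.78; the simulated mean is 2.77.

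**3. Power of the two-step procedure.** Three-arm simulation, 20,000 trials per setting, n=37 per arm. The GLM contains baseline and two binary strata (residual df 3 × 37 − 6 = 105). Two-step means that the omnibus test and the pairwise test are both significant.

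| | R² 0.2 | R² 0.3 | R² 0.5 |
|---|---|---|---|
| Direct t-test | 0.81 | 0.81 | 0.81 |
| Direct GLM contrast | 0.89 | 0.92 | 0.98 |
| Two-step, t-test, equal effects | 0.79 | 0.79 | 0.80 |
| Two-step, GLM contrast, equal effects | 0.86 | 0.91 | 0.98 |
| Two-step, t-test, second diet half effect | 0.75 | 0.77 | 0.79 |
| Two-step, GLM contrast, second diet half effect | 0.81 | 0.86 | 0.95 |
| Mean CI width, GLM contrast (t-test 2.77) | 2.48 | 2.32 | 1.96 |
| Narrower by | 11% | 16% | 29% |
| Omnibus and GLM contrast significant, t-test not | 5–8% | 9–12% | 16–17% |
| Omnibus significant, none of three t-tests significant | 3–4% | 5–7% | 8–13% |

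The ranges in the last two rows span the two effect patterns.

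**4. Low end of R².** At n=36 with equal effects, two-step power with the t-test against the GLM contrast is 75.5% against 75.6% at R² 0, and 75.9% against 79.5% at R² 0.1. At n=37 and R² 0.1, the omnibus test and GLM contrast are significant but the t-test is not in 4.4% of trials (equal effects) or 2.2% (half effect). At R² 0 this happens in under 1%.

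**5. Cost of the omnibus condition alone.** With n=36 and uninformative covariates:

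- Equal effects: omnibus power 0.830; both tests significant 0.753.
- Second diet at half effect: omnibus power 0.704; both significant 0.692.

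Against a direct-test power of 0.797, the losses are about 4 and 10 percentage points. At 37 to 38 completers with equal effects the figure is 0.766 to 0.779. With no drop-out (n=50) it is 0.89 with equal effects and 0.84 with half effect.

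**6. Type I error.** Under no diet effect, the chance of a significant omnibus test followed by any significant t-test cannot exceed that of the omnibus test, simulated at 0.0497. The omnibus condition is a working multiplicity control and is not itself an error.

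**The case against.** **The authors may have meant contrasts from the GLM.** Section 6.1 puts weight change in the GLM and speaks of treatment effects in the next sentence. The fallback (residual method, then Mann-Whitney) also appears to carry adjustment into the pairwise step. This is plausible, but the text names a different, well-defined test and never mentions an adjusted contrast. If GLM contrasts were intended, the wording change below is still needed.

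**The two parts need opposite conditions.** The lost adjustment matters when the covariates are informative; the omnibus condition costs most when they are not. This is correct. With equal effects and R² of 0.2 to 0.5, the two-step t-test is already at 0.79 to 0.80. At R² 0, adjustment gains nothing. The two shortfalls should not be added together.

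**The 0.69 is outside the plan's scenario.** Section 2.1 assumes equal effects, so 0.75 is the figure on its own terms and 0.69 shows sensitivity to that assumption. Section 2.1 also says openly that it sizes a two-group comparison, which makes the power point secondary.

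**The t-test is unbiased under randomisation and has the planned power.** This stands, and it limits the seriousness. Skewed data would also be diverted from the t-test under section 6, and the normal-theory figures above would not apply there.

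**Conclusion.** The concern holds and should be fixed. As worded, sections 6.1 and 6.2 drop the prespecified adjustment from the pairwise diet comparisons, limit the weight-change analysis to the omnibus result, and leave open whether the reported differences are adjusted. This is forgone precision and possible inconsistency; it is not bias, type I error inflation or an underpowered trial.

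The size rests on R², which the SAP does not give: nil at 0, small at 0.1, and material from 0.2 upward. Confidence is medium for that reason and because the authors' intention may differ from their wording.

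The power statement is a lesser point. The 80% is correct for one direct test. It overstates the two-step procedure by about 5 points at n=36 with equal effects and uninformative covariates, and this closes with informative covariates or low drop-out.

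**What to change.** - **Sections 6.1 and 6.2:** replace the independent-samples t-tests with pairwise contrasts from the same fitted GLM, giving adjusted mean difference, 95% CI and p-value. Pool them over imputations wherever the ITT population is analysed. Section 5.2 then inherits the change.
- **Section 6.1:** name customised diet versus control and Nordic diet versus control as the main contrasts, and report the same contrasts from the weight-change model. The omnibus test may stay as the multiplicity control.
- **Section 2.1:** state that the 80% is for a single two-group test without the omnibus condition, or restate power for the two-step procedure together with the R² assumed.

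The cost is SAP wording only: no new participants, data or models, since the contrasts come from a model already being fitted. A restated power figure would be somewhat below 80% at n=36 if no credit is taken for the covariates, and above it if GLM contrasts are used with equal effects and R² of 0.2 or more.

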## 1. Introduction

Randomized controlled studies investigating the impact of replacing dietary carbohydrates with polyunsaturated fat (PUFA) on liver fat content and cardiometabolic risk in individuals with prediabetes and T2D are lacking. Also, the effects of a Healthy Nordic Diet on liver fat content and glycemic control have not been investigated. This study therefore aims to:

- Investigate the effects of the diets on liver fat content (primary aim)
- Investigate the effects of the diets on pancreatic fat, visceral fat, lean tissue, glycemic and lipid control
- Investigate the effects of the diets on plasma markers of de novo lipogenesis (DNL) and desaturation (i.e. stearoyl-Coenzyme desaturase 1, SCD-1) as well as on hepatic DNL using MRI spectroscopy
- Investigate gene-diet interactions, especially if common gene variants (e.g. in PNPLA3) known to increase liver fat and dyslipidemia, may modify the dietary effects.
- Perform lipidomic analyses to identify potential mechanistic pathways that may associate with diet-induced changes in liver fat, pancreatic fat, visceral fat, insulin sensitivity, dyslipidemia or DNL

Our hypothesis is that a customized diet will effectively reduce liver fat through suppression of hepatic DNL and SCD-1 activity, and thereby improve atherogenic dyslipidemia, insulin resistance and hyperglycemia in individuals with prediabetes and T2D.

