## **4. Outcomes**

### **4.1. Primary outcome**

- Between-group changes in liver fat content between baseline and month 12

[Time Frame: 12 months] [Unit: %] [Variable: Continuous]

Assessed by magnetic resonance imaging (MRI)

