## 6. Analyses

Normally distributed variables will be presented as mean  $\pm$  SD and skewed distributed variables will be presented as median (IQR). Continuous variables will be tested for normality using the Shapiro-Wilk W test and skewed data ( $W < 0.95$ ) will be logarithmically transformed or analyzed non-parametrically, where appropriate. Homogeneity of variances between groups will be examined visually. Categorical variables will be presented as counts or percentages (%). An  $\alpha$ -value of 0.05 is set as the significance level.

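### The primary analysis does not name the liver-fat contrast that decides the trial, and its overall-test gate is not the two-group comparison that was powered

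*SAP*

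**What the plan says.** - **Outcome (SAP 4.1).** "Between-group changes in liver fat content between baseline and month 12". There are three diets, and no pair is named.
- **Analysis (SAP 6.1).** A general linear model for the 12-month change in liver fat has diet group as factor and diabetes status, gender and baseline liver fat as covariates. Then: "Independent samples post-hoc t-tests will follow if between-group statistical significance is observed". Pairs, order and multiplicity adjustment are not given. Section 6 sets one level for everything: an alpha "value of 0.05 is set as the significance level".
- **Sample size (SAP 2.1).** "The sample size calculation was based on Lehr's formula for comparison between two groups", "assuming equal treatment effects for the two experimental diets". The target is a 2-point difference "between the control group and one experimental group". Which diet is not said.
- **Hypothesis and aims.** Section 1: "Our hypothesis is that a customized diet will effectively reduce liver fat through suppression of hepatic DNL and SCD-1 activity". This concerns one diet and names no comparator. The primary aim in section 1 refers to the diets in the plural, section 3 lists both the customized and the Nordic diet, and section 2 labels both as experimental with control as active comparator. Section 2 also calls the trial a superiority trial without saying which diet is to be superior to which.

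**The concern.** Three contrasts are available: customized vs control, Nordic vs control, and customized vs Nordic. Each supports a different conclusion, and the SAP does not say which one or ones answer the primary question. The first test asks whether the three diets differ in any way, while the sample size was set for a direct comparison with control.

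Two things follow. A direct contrast that would have been significant is lost when the overall test is not, so the planned power is not delivered. And a significant overall test does not in itself say that either experimental diet is better than control. The follow-up tests add a third mismatch: independent-samples t-tests do not use the baseline and stratification covariates that the model has just adjusted for.

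**Working it through.** **Inputs from the SAP.** Section 2.1: SD of change 3, difference 2 points, 36 evaluable per group, 25% drop-out, 50 randomized per group, power 80% (printed there as beta). Section 6: alpha 0.05. Two-sided testing is assumed, because Lehr's constant of 16 corresponds to two-sided 5% and 80% power.

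**The SAP's own figure.** Lehr: 16 × (SD/difference)² = 16 × (3/2)² = 36 per group. With drop-out, 36/0.75 = 48, so 50 is enough. By the normal approximation, 36 per group gives 80.7% power. The arithmetic is right, but for an ungated two-group test.

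**Why the gate costs power.** The direct test has squared noncentrality 2²/(2 × 9/36) = 8. The overall test has noncentrality n × Σ(μ − mean)²/SD², on 2 degrees of freedom. Effects relative to control are written customized/Nordic.

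- −2/0 and −2/−2: Σ = 24/9, so 36 × (24/9)/9 = 10.7.
- −2/−1: Σ = 2, so 36 × 2/9 = 8. This is the same signal as the direct test, spread over 2 degrees of freedom.

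**Simulation of the written rule.** Overall F-test at 5%, then t-tests at 5% without multiplicity adjustment; 36 per arm, SD 3, no covariates, 40,000 runs per row.

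| Effects (customized/Nordic) | Overall test significant | Customized better than control, direct test | Same, behind the gate |
|---|---|---|---|
| −2/−2 (SAP 2.1 assumption) | 82.9% | 79.6% | 75.2% |
| −2/0 | 83.0% | 80.0% | 75.4% |
| −2/−1 | 70.4% | 79.7% | 69.1% |

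**Type I error.** With no true differences, the gated procedure declares at least one pair in 5.1% of runs. If only one pair is truly equal, a single true null remains, tested at 5%. Without the gate, any of the three pairs would be significant in about 12% of runs.

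**What a significant overall test can rest on.** Under the SAP's equal-effects case (−2/−2), it occurs with neither diet better than control in about 0.0% of runs. Under an assumed divergence of −1/+1, the overall test is significant in about 70% of runs. In about 43% of all runs it is significant with neither diet better than control. In about 19% neither differs from control in either direction, and the result rests on customized vs Nordic alone.

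**Alternatives under the same inputs.**

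| | Current gate | Fixed order, customized first | Holm on two control contrasts |
|---|---|---|---|
| Customized vs control, −2/0 | 75% | 80% | 71% |
| Each contrast, −2/−2 | 75% | 80% first, 68% second | 76% |
| Nordic vs control, 0/−2 | 75% | about 3% | 71% |

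**The case against.** The strongest defence is that an overall test with pairwise follow-up is a conventional match to the aims. Sections 1 and 3 ask about both diets, section 2 labels both as experimental, and section 2.1 assumes equal effects. With three groups the gate controls the family, so a significant Nordic result would be reported as a Nordic result, and correctly so. This stands on two counts. Error control is adequate, and the SAP does not oblige the sponsor to rank the customized diet first: the section 1 hypothesis is one sentence among several that give both diets standing.

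A reader might infer that the plan lets the trial be called positive although no experimental diet has beaten control. The documents do not support that. The SAP contains no rule for calling the trial positive, and it does not say that all pairs have equal standing. Under its own equal-effects assumption that pattern practically never occurs, and the −1/+1 case is an assumption that departs from section 2.1. A reader might also take the 12% figure as the plan's error rate. It applies only if intervals are read as tests outside the gate, which section 6.1 does not say.

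The defence does not reach the mismatch with section 2.1. A direct two-group test was powered and a gated one is planned, with the contrast that decides left unnamed.

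**Conclusion.** The point holds as a gap in specification with a measurable power cost. The outcome variable, time point, model and covariates are fixed; the deciding contrast and its multiplicity rule are not. Relative to the planned 80%, the gate costs about 4 to 5 percentage points when Nordic has an effect of 0 or −2, and about 11 when Nordic has −1. These figures rest on SD 3, 36 evaluable per arm, two-sided 5% tests, no covariates and, apart from −2/−2, assumed effects. They concern the general linear model branch, not the fallback for failed model assumptions. Neither inflated type I error nor a stated wrong success rule is shown. The change should be made because this analysis determines what the trial may claim.

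**What to change.** In SAP 4.1 and 6.1:

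1. Name the diet-vs-control contrast or contrasts as primary: 12-month change in liver fat, estimated from the covariate-adjusted model in the ITT population. Report estimate, 95% confidence interval and p-value from that model, not from separate t-tests.
2. Make customized vs Nordic secondary. The overall test may stay as supportive, but not as a gate.
3. State the multiplicity rule before unblinding. The ranking is the sponsor's choice:
   - a fixed order at two-sided 5% per step if one diet ranks first (customized first fits the section 1 hypothesis);
   - Holm over the two control contrasts if both rank equally (fits sections 2 and 3).
4. Restate the power in section 2.1 to match the rule chosen.

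**Cost.** Wording only, with no new data. Under a fixed order the second diet cannot be claimed if the first fails, and 36 evaluable per group remains sufficient for the first contrast. Under Holm the smaller p-value is tested at 2.5%, with about 71% power without covariates for a single effective diet and about 76% per contrast if both work. Reaching 80% per contrast at 2.5% without covariates would take 43 evaluable per group, or 58 randomized (43/0.75 = 57.3), 174 in total. Covariate adjustment would make up that gap at 36 per group if the covariates explain about 16% of the variance of the change (1 − 36/43 = 0.16). The SAP gives no figure for that share.

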## **6.2 Secondary and exploratory outcomes**

For secondary and exploratory outcomes GLMs will be applied using  $\Delta$ values between baseline and month 12 for each continuous variable (see point 4.2 and 4.3) as dependent variables and type-2 diabetes status (yes/no), gender (male/female) and baseline outcome values as included covariates in the model. Outcome values from 6 months follow-up will be presented descriptively.

The GLM will be applied for the ITT-population (defined above) as well as for the PP-population (defined above) for HbA1c, LDL cholesterol, triglycerides and systolic- and diastolic blood pressure. For the remaining secondary and exploratory outcomes, a PP-population will be used. Independent samples post-hoc t-tests will follow if between-group statistical significance is observed.

Treatment effects will be presented as mean or median differences (%) with 95% confidence intervals and with corresponding p-values.

When assumptions of the GLM are not satisfied, the Willett's residual method will be applied (3), followed by Mann-Whitney U post-hoc tests.

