## **3. Aims and objectives**

The overall aim of this study is to investigate the long-term impact of a customized diet aimed at reducing liver fat specifically and a healthy Nordic diet on ectopic fat (liver, pancreatic and visceral) and cardiometabolic risk in individuals with prediabetes and type 2 diabetes.

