### **4.2. Secondary outcomes**

- Between-group changes in visceral adipose tissue mass between baseline and month 12

[Time Frame: 12 months] [Unit: L] [Variable: Continuous]

Assessed by magnetic resonance imaging (MRI)

- Between-group changes in lean tissue mass between baseline and month 12

[Time Frame: 12 months] [Unit: L] [Variable: Continuous]

Assessed by magnetic resonance imaging (MRI)

- Between-group changes in total body fat mass between baseline and month 12  
 [Time Frame: 12 months] [Unit: L] [Variable: Continuous]  
 Assessed by magnetic resonance imaging (MRI)
- Between-group changes in body weight between baseline and month 12  
 [Time Frame: 12 months] [Unit: kg] [Variable: Continuous]  
 Assessed by using a Tanita bioelectrical impedance analysis (BIA) scale
- Between-group changes in glycated hemoglobin (HbA1c) between baseline and month 12  
 [Time Frame: 12 months] [Unit: mmol/mol] [Variable: Continuous]  
 Assessed by routine clinical chemistry
- Between-group changes in Homeostatic Model Assessment for Insulin Resistance (HOMA-IR) between baseline and month 12  
 [Time Frame: 12 months] [Unit: none] [Variable: Continuous]  
 Calculated by multiplying fasting plasma glucose (mmol/L) with fasting serum insulin (mU/L) and dividing the product by 22.5.  
 Assessed by routine clinical chemistry
- Between-group changes in fasting plasma glucose between baseline and month 12  
 [Time Frame: 12 months] [Unit: mmol/L] [Variable: Continuous]  
 Assessed by routine clinical chemistry
- Between-group changes in fasting serum insulin between baseline and month 12  
 [Time Frame: 12 months] [Unit: mU/L] [Variable: Continuous]

Assessed by routine clinical chemistry

- Between-group changes in systolic blood pressure between baseline and month 12

[Time Frame: 12 months] [Unit: mmHg] [Variable: Continuous]

Assessed by using an automated blood pressure monitor

- Between-group changes in diastolic blood pressure between baseline and month 12

[Time Frame: 12 months] [Unit: mmHg] [Variable: Continuous]

Assessed by using an automated blood pressure monitor

- Between-group changes in plasma lipids (total cholesterol, LDL cholesterol, triglycerides, HDL cholesterol, apoB and apoA1) between baseline and month 12

[Time Frame: 12 months] [Unit: mmol/L or g/L (apoB and apoA1)] [Variable: Continuous]

Assessed by routine clinical chemistry

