- Between-group changes in circulating inflammatory markers (CRP, Tumor Necrosis Factor Alpha-receptor 1 and 2, Interleukin-1 receptor antagonist, Fibroblast growth factor 21) between baseline and month 12

[Time Frame: 12 months] [Unit: ng/l or mg/l (CRP)] [Variable: Continuous]

Assessed by routine clinical chemistry and ELISA

- Between-group changes in pancreatic fat between baseline and month 12

[Time Frame: 12 months] [Unit: %] [Variable: Continuous]

Assessed by magnetic resonance imaging (MRI)

- Between-group changes in flow-mediated dilation (FMD) between baseline and month 12

[Time Frame: 12 months] [Unit: %] [Variable: Continuous]

Assessed by ultrasound in approximately half of the study population (n=75)

- Between-group changes in pulse-wave velocity (PWV) between baseline and month 12  
[Time Frame: 12 months] [Unit: m/s] [Variable: Continuous]

Assessed by ultrasound in approximately half of the study population (n=75)

- Between-group values in FMD and PWV at month 12  
[Unit: % and m/s] [Variable: Continuous]

Assessed by ultrasound in the whole population (n=150)

- Between-group changes in liver fat, HbA1c, and blood lipids in prespecified subgroups of type-2 diabetes status (yes/no), gender (male/female), individuals with NAFLD/without NAFLD at baseline, individuals with the CC vs CG/GG I148M genotype in PNPLA3, and in individuals with low respectively high dietary compliance based on dietary and lipogenic biomarkers changes (e.g. linoleic acid, DHA and palmitoleic acid changes from baseline to 12 months) between baseline and month 12

[Time Frame: 12 months]

We will assess whether response to diets in liver fat, HbA1c and blood lipids differ between gender, high vs low compliers, genotype, individuals with prediabetes or diabetes or those who have NAFLD/do not have NAFLD at baseline

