### **5. Populations and subgroups to be analyzed**

#### **5.1 Populations**

**Intention to treat (ITT):** All subjects randomized at baseline will constitute the ITT-population and will be the primary study population for the analyses. Missing data will be imputed as described in section 7 in this document.

**Per-protocol (PP):** All subjects completing the study period with complete data on the outcome of interest will constitute the PP-population. The PP-population will be the secondary study population for the analyses.

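### Section 6.2 leaves 19 of 24 secondary change variables with a completers-only analysis, an unexplained exception to the population ranking in section 5.1

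*SAP*

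**What the plan says.** Section 5.1 ranks the two populations in general terms. All randomised subjects, with missing data imputed, "will constitute the ITT-population and will be the primary study population for the analyses". "The PP-population will be the secondary study population for the analyses". It defines the second set as follows: "All subjects completing the study period with complete data on the outcome of interest will constitute the PP-population". There is no adherence criterion, so PP is a completers set formed outcome by outcome.

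Section 6.2 applies both populations to HbA1c, LDL cholesterol, triglycerides, and systolic and diastolic blood pressure. Then: "For the remaining secondary and exploratory outcomes, a PP-population will be used". No reason is given for the choice of these five.

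Three other places bear on this:

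- Section 4.2 lists the six lipids as one secondary outcome: "Between-group changes in plasma lipids (total cholesterol, LDL cholesterol, triglycerides, HDL cholesterol, apoB and apoA1").
- Section 5.2 says of the subgroups: "All subgroup analyses will be conducted as described for the analyses of the full study population".
- Section 7 prescribes MICE for dependent and explanatory variables and names no outcomes to which it is limited.

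**The concern.** For most secondary outcomes, the population that section 5.1 ranks second becomes the only one. These include visceral and pancreatic fat, which belong to the overall aim in section 3, where the SAP names the effect of the customised diet and "a healthy Nordic diet on ectopic fat (liver, pancreatic and visceral) and cardiometabolic risk". Neither has an analysis in the population that the SAP itself calls primary.

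The statistical stake is selection. A completers-only contrast adjusted for baseline is not protected by randomisation if the participants who leave differ in response, and differ in another way in one arm than in another. Section 2.1 allows for 25% drop-out, so the excluded share may not be small. The reporting stake is that a reader would find two lipids with an all-randomised estimate and four without, and no explanation.

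**Working it through.** **Count of secondary change variables (section 4.2) against section 6.2**

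| Block | Variables | ITT plus PP | PP only |
|---|---|---|---|
| Visceral fat, lean tissue, total body fat, body weight | 4 | 0 | 4 |
| HbA1c, HOMA-IR, fasting glucose, fasting insulin | 4 | 1 | 3 |
| Systolic and diastolic blood pressure | 2 | 2 | 0 |
| Plasma lipids | 6 | 2 | 4 |
| Inflammatory markers | 5 | 0 | 5 |
| Pancreatic fat | 1 | 0 | 1 |
| FMD and PWV change | 2 | 0 | 2 |
| **Total** | **24** | **5** | **19** |

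- 24 − 5 = 19, and 19/24 = 79%.
- FMD and PWV change are restricted by design: "Assessed by ultrasound in approximately half of the study population (n=75"). Without them, 22 − 5 = 17 PP-only variables.
- With the month-12 values of FMD and PWV, which are not changes, 26 − 5 = 21.
- The exploratory changes are also PP-only and are not in this count.

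**Sample size and participants left out**

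The plan's own figure reproduces: Lehr's formula gives 16/(2/3)² = 36 per group, and 36/0.75 = 48, close to the planned 50. At 25% drop-out, 0.25 × 150 = 37.5 leave and 112.5 remain. A PP-only outcome would rest on about 112 participants, against 150 in ITT.

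**Consistency inside the SAP**

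- Lipids: all six are analysed in PP. Only LDL cholesterol and triglycerides are also analysed in ITT. Through section 5.2 the same difference enters every lipid subgroup.
- Body weight: section 6.1 adds weight change as a covariate to the ITT model for liver fat, and section 7 imputes explanatory variables. Weight change must therefore already be imputed for all randomised participants. As an outcome in its own right it is analysed in completers only.

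**Illustration of possible bias (assumptions, not from the SAP)**

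The set-up is two arms of 500,000, true effect zero, 25% drop-out per arm, and a GLM adjusted for baseline. Drop-out is logistic in the 6-month change, with slope 0.5, 1 or 1.5 per SD (odds ratio 1.6, 2.7 or 4.5). The 6-to-12-month correlation is 0.7 or 0.5, and the baseline-change correlation is 0 or −0.3. Bias is in SD of the 12-month change.

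| Drop-out depends on | Correlation 0.7 | Correlation 0.5 |
|---|---|---|
| Response in one arm only, slopes 0.5 / 1 / 1.5, baseline-change correlation 0 | 0.08 / 0.15 / 0.20 | 0.06 / 0.11 / 0.14 |
| Same, baseline-change correlation −0.3 | 0.07 / 0.13 / 0.17 | 0.04–0.05 / 0.09 / 0.12 |
| Response in both arms, slopes 1 and 0.5 | 0.06–0.07 | 0.04–0.05 |
| Response equally in both arms, or baseline only | below 0.01 | below 0.01 |

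What imputation does to these figures:

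- On baseline covariates alone, the estimate is the same as in completers.
- With the 6-month value, if every drop-out has one, bias is below 0.01.
- With the 6-month value, if half of the drop-outs leave before month 6, about 40–45% of the bias remains. For slope 1 at correlation 0.7 and baseline-change correlation 0, about 0.15 falls to 0.06–0.07.
- If all leave before month 6, none is removed.

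**The case against.** The strongest reply is that section 6.2 is specific and governs the general sentences in section 5.1. No analyst could run the wrong analysis, and section 7 can be read as applying wherever ITT is used. This stands. A reader might infer that the SAP is ambiguous about which population applies; it is not. What remains is an exception that section 5.1 does not announce and for which no reason is given.

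A reader might also infer that the six lipids are placed in separate populations and cannot be compared. They can: all six have a PP analysis, so a like-for-like comparison exists in completers. It is the ITT analysis that two have and four lack.

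Nor is the fuller treatment of MRI liver fat, compared with MRI visceral or pancreatic fat, evidence of an arbitrary choice. Liver fat is the primary outcome and comes under section 6.1.

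On harm, the objection is largely right. The SAP gives no drop-out mechanism, and 25% is an allowance. The figure of 0.20 SD needs response-dependent drop-out in one arm only, at the strongest slope and the higher correlation. Moving to ITT without 6-month values would remove none of this bias, so the gain depends on section 7 as much as on section 6.2. Outcome values from 6 months are planned for descriptive use, but the SAP does not say whether MRI is among them. For visceral and pancreatic fat the gain is therefore undemonstrated.

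**Conclusion.** The point holds as an unexplained and unreconciled exception: 19 of 24 secondary change variables (17 of 22 without FMD and PWV change) have no analysis in the SAP's own primary population. The count follows from the text and needs no assumption. The treatment of body weight shows that the necessary imputation is already planned for at least one of these variables.

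The size of any resulting bias cannot be determined from the SAP. The illustrative 0.05 to 0.20 SD (0.04 in the mildest cases) rests on assumed drop-out that depends on response unequally between arms. It is about zero if that dependence is equal or is on baseline only. The documents do not support a claim that the secondary results will be biased, and the point does not touch the primary analysis, which has both ITT and PP. It is a cheap improvement of minor to moderate severity.

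**What to change.** - **Section 6.2:** analyse the remaining secondary outcomes in ITT first, using the MICE already planned, and in completers second, as section 5.1 ranks them. For FMD and PWV change, do this within the subset measured at baseline. All six lipids, and their subgroup analyses through section 5.2, are then handled alike.
- **Section 7:** state that 6-month values, where collected, enter the imputation model as auxiliary predictors. Without this step the change of population does not reduce the bias described.
- **If some outcomes are to stay completers-only:** say so in sections 5.1 and 7, give the reason, and treat the six lipids the same way.

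The cost is SAP wording and a larger imputation model, which may have to be run by outcome block with 150 participants. Little bias reduction can be expected for participants who leave before month 6 or for outcomes without a 6-month measurement.
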